8. STUDY OBJECTIVES

8.1 Primary Objective

To evaluate the efficacy of open-label ganaxolone as adjunctive therapy for uncontrolled seizures in children with PCDH19 Female Pediatric Epilepsy, CDKL5 Disorder, Dravet Syndrome, and other epileptic syndromes such as LGS, CSWS and other potential genetic or clinical conditions with or without corresponding genetic condition (referred to as genetic epilepsies) in an open-label proof-of-concept study.

8.2 Secondary Objectives

To evaluate the safety and tolerability of open-label ganaxolone as adjunctive therapy for uncontrolled seizures in children with genetic epilepsies.

9. INVESTIGATION PLAN

9.1 Overall Study Design and Plan

The purpose of this proof-of-concept study is to evaluate ganaxolone as adjunctive therapy for uncontrolled seizures in female children with PCDH19 mutations, CDKL5 mutation and SCN1A mutation (Dravet syndrome) and other epileptic syndromes such as LGS, CSWS and other potential genetic or clinical conditions with or without corresponding genetic condition (referred to as genetic epilepsies) in an open-label proof-of-concept study. After establishing baseline seizure frequency, qualifying subjects will enter the study and be treated with open-label ganaxolone oral suspension or ganaxolone capsules at doses up to a maximum of 1800 mg/day for up to six months. Maximum study participation will be 94 weeks: a screening period to establish baseline seizure frequency, 26 weeks treatment, and a 52 week extension for patients who benefit from ganaxolone treatment and up to 4 weeks down-titration.

9.2 Discussion of Study Design

This proof-of-concept study was designed to evaluate ganaxolone in a small number of pediatric subjects with open-label treatment. The open-label design eliminates exposure to placebo, and the flexible dose selection allows optimization of the dose for these pediatric subjects. Administration of the test article as adjunctive therapy to background antiepileptic drugs (AEDs) provides standard-of-care therapy in addition to any benefit that study medication might provide.

9.3 Selection of study population

9.3.1 Number of Subjects

Approximately 10 subjects with PCDH19, 10 subjects with CDKL5 Disorder, 10 subjects with Dravet Syndrome, and up to 10 subjects with LGS, CSWS, encephalopathic epilepsy or other genetic epilepsy cases will participate.

9.3.2 Inclusion Criteria

- 1. Have parent or legal guardian available and willing to give written informed consent, after being properly informed of the nature and risks of the study and prior to engaging in any study-related procedures.
- 2. Outpatients between 2 and 18 years of age at time of consent.

3. In the opinion of the investigator have confirmed PCDH19 genetic mutation, confirmed CDKL5 genetic mutation or Dravet Syndrome confirmed by a SCN1A mutation, or genetic epilepsy testing confirming a LGS or CSWS condition associated with this genetic phenotype. Refractive cases of LGS or CSWS that remain idiopathic or have prior history of steroid or ACTH response can also be entered if documentation confirms specific genetic defects are not found and prior steroid response clinically occurred.

4. Seizure criteria:

- a. Have uncontrolled cluster seizures (3 or more seizures over the course of 12 hours) every 6 weeks or less during baseline, or bouts of status epilepticus on intermittent basis, or
- b. Have uncontrolled non-clustered seizures (focal dyscognitive, focal convulsive, atypical absences, hemiclonic seizures, spasms, or tonic-spasm seizures) with a frequency ≥4 seizures per 28-day period during baseline, or
- c. Have ≥4 generalized convulsive (tonic-clonic, tonic, clonic, atonic seizures) per 28-day baseline period during baseline, or
- d. Have subclinical CSWS syndrome with or without clinical events on EEG
- 5. Subjects should be on a stable regimen of AED medication, and generally in good health.
- 6. Parent or guardian is able and willing to maintain an accurate and complete daily written seizure calendar for the duration of the study.
- 7. Able and willing to take study medication with food, two or three times daily. Ganaxolone must be administered with food.
- 8. Sexually active women of child bearing potential (WCBP) must be using a medically acceptable method of birth control and have a negative urine sample at the baseline visit. A woman of childbearing potential is defined as a female who is biologically capable of becoming pregnant. A medically acceptable method of birth control includes intrauterine devices in place for at least 3 months, surgical sterilization, or adequate barrier methods (e.g., diaphragm and foam). An oral contraceptive alone is not considered adequate for the purpose of this study. Use of oral contraceptives in combination with another method (e.g., a spermicidal cream) is acceptable. In subjects who are not sexually active, abstinence is an acceptable form of birth control and urine will be tested per protocol.
- 9. Subject must be approved to participate by Sponsor and Principal Investigator

after review of medical history and baseline seizure calendars.

10. For entry into the 52 week open label extension, subjects must have completed all scheduled clinical study visits and have shown a minimum 35% improvement in mean seizure frequency per 28 days vs. baseline over the 28 day periods preceding study entry.

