Subjects should be on a stable regimen of AED medication, and generally in good health without active central nervous system (CNS) infection or progressive disease or clinically unstable psychiatric disorder likely to require new treatment during the study Subjects who have completed all scheduled clinical study visits and have shown a minimum 35% improvement in mean seizure frequency per 28 days vs. baseline may be enrolled in the 52 week open label extension.

Number of Subjects: Approximately ten (10) subjects with PCDH19, 10 subjects with CDKL5 Disorder, 10 subjects with Dravet Syndrome, and up to 10 subjects with LGS, CSWS, encephalopathic epilepsy or other genetic epilepsies will be enrolled.

Test Product, Dose and Mode of Administration: Ganaxolone oral suspension 50 mg/mL dosed TID, or ganaxolone 200 mg or 225 mg capsules administered in BID. Oral suspension or capsules to be administered up to a total of 63 mg/kg/day but not more than 1800 mg/day.

Duration of Treatment: After establishing baseline seizure type and frequency for a minimum of 4 weeks and up to 12 weeks, subjects entering the study will be treated with ganaxolone for 26 weeks, in the main portion of the study, and up to an additional 52 weeks if clinical response is established plus additional time to down-titrate (1 to 4 weeks).

Reference Therapy, Dose and Mode of Administration: Not applicable

Criteria for Evaluation:

Primary Efficacy: Primary efficacy will be percent change in seizure frequency (focal dyscognitive or focal convulsive) per 28 days relative to the baseline.

Secondary Efficacy: Secondary efficacy assessments include evaluation of intercluster interval, time to reach baseline number of seizures, seizure-free interval, 50% responder proportion, proportion with 50% increase in inter-cluster interval, CGI-I.

Safety: Neurological and physical examinations, clinical laboratory tests, electrocardiogram (ECG), vital signs, EEG and spontaneously reported adverse events (AEs).

Serum Levels: Blood samples will be drawn at baseline, 2 weeks, 8 weeks, 26 weeks and at each visit in the open labeled extension and at unscheduled visits as needed for evaluation of blood chemistry and hematology, and to measure levels of ganaxolone, concomitant AED medications, allopregnanolone, and related endogenous CNS-active steroids.

Statistical Methods:

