9.5 Efficacy and Safety Variables

9.5.1 Calculation of Baseline

Baseline will be calculated from a maximum of 12 weeks' of seizure calendar data with a minimum of 4 weeks of data required, which should include contiguous retrospective ratings provided after signing informed consent. Acceptable retrospective daily seizure

data include a diary record of the frequency and type of seizures by day. Source data may include a seizure diary or calendar, recorded data from smart phones or other devices. Seizure clusters are to be identified, and the number of seizures in the daily cluster should be counted or given as best estimate.

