6. EFFICACY ANALYSES

All efficacy analyses will be summarized by cohort in the MITT population. These summaries will include only the CDKL5, LGS, and PCDH19 cohorts since only 2 patients were enrolled in the CWS cohort. However, the CWS cohort will be included in the subject data listings. For the analyses of seizures and clusters, the baseline period consists of up to 12 weeks before the first day of treatment, and the 26-week open-label treatment period starts with the day following the first day of treatment until the final visit for subjects who do not enter the OLE and up to the day before the first dose of OLE treatment for those who do. The first day of treatment is not in either period since the times of seizures were not collected.

Seizure diary compliance will be summarized by cohort. The calculated compliance is:
 $100 \times (\text{Number of Days with Available Seizure or Cluster Diary}) / (\text{Last Available Seizure or Cluster Diary Date} - \text{First Available Seizure or Cluster Diary Date} + 1)$.

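### A single cluster in a 4-week baseline cannot establish the 6-week interval in criterion 4a, so cluster-only children can look improved with no drug effect

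*Protocol*

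**What the plan says.** Protocol 9.3.2, criterion 4a, admits children with uncontrolled clusters "every 6 weeks or less during baseline". A second limb of the same item admits children by another route: "or bouts of status epilepticus on intermittent basis". Criteria 4b and 4c are stated per 28 days.

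Protocol 9.5.1 caps baseline at 12 weeks, "with a minimum of 4 weeks of data required". It lets past diary data count: "contiguous retrospective ratings provided after signing informed consent". SAP section 6 says "the baseline period consists of up to 12 weeks before the first day of treatment" and restates no minimum.

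Inclusion criterion 9 requires the sponsor and Principal Investigator to approve each child "after review of medical history and baseline seizure calendars". Neither document says how many clusters are needed, or how a 6-week interval is to be judged from a shorter record.

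The same baseline is the denominator for the SAP's primary endpoint (6.1: individual seizures plus clusters, each cluster counted once), cluster frequency (6.2.2) and the 25%, 50% and 75% responder proportions (6.2.9). It is also the reference for the 35% improvement needed to enter the extension (inclusion criterion 10). SAP 1.3.2 confirms that there is no control group.

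**The concern.** The 28-day criteria 4b and 4c fit a 4-week minimum; the 6-week criterion does not. A child with one cluster in 28 days offers no interval between clusters, yet nothing stops that cluster from being taken as meeting 4a.

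The consequence goes beyond eligibility. A child who enters because a cluster fell inside a short window carries a baseline rate of at least 1 per 4 weeks, even if the true rate is lower. Over the following 26 weeks the observed rate tends back to its true level. With no control arm, that fall cannot be told apart from a drug effect in cluster frequency or, for children with few individual seizures, in the primary and responder results.

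**Working it through.** The plan gives no figure to reproduce: Protocol 9.7.8 states about 10 subjects per cohort without a derivation.

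**Inputs from the documents.** Baseline minimum 28 days and maximum 84 (Protocol 9.5.1); treatment 26 weeks = 182 days (Protocol synopsis: "subjects entering the study will be treated with ganaxolone for 26 weeks"); percent change as in SAP 6.1.

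**Assumptions, not in the documents.** Clusters follow a Poisson process with true mean interval T, shown from 4 to 12 weeks. There is no drug effect. A child enters on at least one cluster in the window.

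**Step 1: what one cluster shows.** The exact 95% interval for a Poisson mean with one event is 0.0253 to 5.572. Over 4 weeks the mean cluster interval is therefore between 4/5.572 = 0.7 weeks and 4/0.0253 = 158 weeks. The chance of at least one cluster in 28 days is 1 − exp(−4/T): 49% at T = 6, but also 39% at T = 8 and 28% at T = 12, both less frequent than 4a asks.

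**Step 2: cluster frequency under no effect.** Let X be the baseline count with mean μ = (baseline weeks)/T, and Y the treatment count with mean 26/T.

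- Mean change = μ × E(1/X | X ≥ 1) − 1. With T = 6 and 4 weeks, μ = 0.667 and E(1/X | X ≥ 1) = 0.840, so the change is 0.667 × 0.840 − 1 = −44%.
- A 50% responder needs Y/26 ≤ 0.5 × X/4, that is Y ≤ 3.25X, with Y having mean 26/6 = 4.33. For X = 1, P(Y ≤ 3) = 0.371; for X = 2, P(Y ≤ 6) = 0.852; for X = 3, P(Y ≤ 9) = 0.987. Given X ≥ 1, these counts have probabilities 0.703, 0.235 and 0.052, with 0.010 left for X ≥ 4. The sum is 0.261 + 0.200 + 0.051 + 0.010 = 0.522.
- With exactly one cluster, the mean change is μ − 1 = −33% and the responder chance is 37%.

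The same calculation over the range:

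| Baseline and entry rule | T (weeks) | Mean change | False 50% responders |
|---|---|---|---|
| 4 weeks, at least 1 | 4 | −23% | 33% |
| 4 weeks, at least 1 | 6 | −44% | 52% |
| 4 weeks, at least 1 | 8 | −56% | 68% |
| 4 weeks, at least 1 | 12 | −69% | 85% |
| 4 weeks, exactly 1 | 4 | 0% | 11% |
| 4 weeks, exactly 1 | 6 | −33% | 37% |
| 4 weeks, exactly 1 | 8 | −50% | 59% |
| 6 weeks, at least 1 | 4 | −0.1% | 25% |
| 6 weeks, at least 1 | 6 | −23% | 39% |
| 6 weeks, at least 1 | 8 | −38% | 52% |
| 12 weeks, at least 2 | 4 | −2% | 20% |
| 12 weeks, at least 2 | 6 | −23% | 35.5% |
| 12 weeks, at least 2 | 8 | −38% | 50% |

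At T = 6 with 4 weeks and at least one cluster, 69% of cluster-only children would also show a fall of 35% or more.

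**Step 3: the SAP primary endpoint.** Individual seizures were added as an independent Poisson count (simulation, 400,000 children per setting before selection; T = 6, 4-week baseline, at least one cluster).

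| Individual seizures per 28 days | Median change | False 50% responders |
|---|---|---|
| 0 | −54% | 52% |
| 1 | −23% | 25% |
| 3 | −13% | 11% |
| 10 | −5% | 1% |

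**Step 4: scale.** Ten cluster-only children at T = 6 would give 10 × 0.522 = 5.2 false 50% responders on average.

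**The case against.** Several points on the other side stand.

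- A reader might infer that a 4-week baseline can never show the interval. Two clusters within 4 weeks do show one under 6 weeks. Four weeks is only the floor, past diaries count, and the sponsor and Principal Investigator review each child's history. The gap is that none of this sets a rule for a child with one cluster.
- A reader might infer that children admitted on one cluster will be counted as responders. With exactly one cluster, most children within the criterion are not: 37% at one per 6 weeks and 11% at one per 4 weeks.
- A reader might note that a child at one per 6 weeks has no cluster in 4 weeks 51% of the time, and infer that about half of the percent changes are undefined. A child with no baseline cluster does not meet the cluster limb, so this is not a rate among children enrolled through it.
- The primary and responder endpoints include individual seizures, which dilute the effect sharply. The documents do not say how many children are cluster-only. Protocol section 7 calls clusters the hallmark of PCDH19 epilepsy but adds that individual seizures also occur.
- Regression to the mean is expected in an open, uncontrolled proof-of-concept study. The results are descriptive, with individual data shown and no test or success threshold. That limits the harm, but no planned output shows how far an apparent response rests on a short baseline.
- The SAP cites Amendment 8.1 (August 2017), while the supplied protocol's history ends at V6.0 (April 2016). The wording of 4a or 9.5.1 may have changed. The SAP also describes enrollment as past, so a new entry rule may come too late for these data.

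**Conclusion.** The point holds in a limited form. The 4-week minimum is shorter than the interval in 4a, a single cluster in 4 weeks cannot establish that interval, and the qualifying window is reused as the denominator with no control arm. Children with clusters and few or no individual seizures can therefore look improved without a drug effect. At a true one per 6 weeks the size is −44% and 52% false 50% responders on at least one cluster. It is smaller at higher true rates (−23% and 33% at one per 4 weeks) and larger at lower ones. It largely disappears from the primary and responder results at about 10 individual seizures per 28 days, but cluster frequency stays exposed.

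These figures rest on Poisson counts and assumed true rates. Bunching of clusters in time, or entry timed to a bad spell, would make the artefact larger.

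The calculation does not show that a full 12 weeks is necessary. At one per 6 weeks, 12 weeks with at least two clusters (−23%, 35.5%) is close to 6 weeks with at least one (−23%, 39%).

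**What to change.** First check 4a and 9.5.1 in the protocol amendment that the SAP cites.

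- **Protocol 9.5.1:** for children who qualify only through the cluster limb of 4a, require at least 6 weeks of baseline calendar data, and preferably up to the 12 weeks already allowed, with past diary days counting as now. The status epilepticus limb has no 6-week interval and is not part of this change.
- **SAP 6.1, 6.2.2 and 6.2.9:** summarize baseline length by cohort. Repeat the primary, cluster-frequency and responder tables in subjects with a longer baseline, for example at least 8 weeks, as a descriptive sensitivity analysis.

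The cost is a few more weeks of charting for a cluster-only child without a past diary, plus some extra tables. In cohorts of about 10 the subsets will be small. The SAP part needs no new data and can be done even if enrollment is complete. A 6-week minimum reduces the artefact but does not remove it, because the qualifying window remains the denominator.

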Neurological Examination ¹	X	X	X	X	X	X	X	X
Safety Labs (Blood ⁷ and Urine ²)		X			X		X	X
Urine Pregnancy Test (WCBP)		X		X	X	X	X	
Administer C-SSRS		X	X	X	X	X	X	X
EEG		X ⁹		X ⁹	X	X	X ⁹	
Review safety and record AEs			X	X	X	X	X	X
Efficacy Assessments								
Instruct/ Provide Seizure Calendar	X	X	X	X	X	X	X	X
Subject Calendar Review	X	X	X	X	X	X	X	X
Complete CGII-C				X	X	X	X	
Instruct and Collect CGII-P				X	X	X	X	
Other Assessments								

Week	0	2	4	8	17	26		
Visit	V1 Screening	V2 Baseline	V3 ± 3 days	V4 ± 3 days	V5 ± 3 days	V6 ± 7 days	V7 Final Visit ⁴ ± 7 days	Unscheduled Visit or Dose Escalation Visit ⁶
VAS		X			X		X	
PK/PD Assessments								
Concomitant AED medications		X			X		X	
Study Drug Blood Samples					X		X	
Neurosteroid levels		X			X		X	
Study Medication								
Dispense Medication	X	X ³	X ³					
Collect bottles from prior visit study medication		X	X	X	X	X	X	X
Instruct on Down-titration							X ⁸	

AEs = adverse events; AED = antiepileptic drug; CGII-C = Clinical Global Impression of Improvement-Clinician; CGII-P = Clinical Global Impression of Improvement-Parent/Guardian; C-SSR = Columbia Suicide Severity Rating; ECG = electrocardiogram; EEG = Electroencephalography; VAS = Visual Analogue Scale; WBCP=women of childbearing potential

- 1 Physical and neurological exam records performed at the same center within 60 days of screening visit may be used in place of screening exam. Visits 3, 4, 5 and 6 may be follow-up exams. Tanner Scores will be collected.
- 2 Obtain urine sample for those who are toilet trained.
- 3 Adjust dose if necessary.
- 4 This visit could also be an Early Termination visit. The subject should be instructed on down-titration and should be scheduled for the Follow-up Visit (V11) when down-titration has been completed. At this visit, investigator confirms if the subject qualifies for the 52-week extension, subjects must have completed all scheduled clinical study visits and have shown a minimum 35% improvement in mean seizure frequency per 28 days vs. baseline.
- 5 Vital signs including temperature, blood pressure, pulse, and weight. Height will be measured at Visit 1 (Screening) only.

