2.5 HANDLING OF MISSING DATA

Unless otherwise specified, missing data will not be imputed. All analyses will be based on available data.

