9. ANALYSIS OF OPEN-LABEL EXTENSION PERIOD

Baseline for the OLE period is the same as for the main period. The key background and efficacy tables to be provided for the main 26-week open-label treatment period of the study will also be provided for the 52-week OLE. These include:

- Subject disposition
- Demographics and baseline characteristics
- Concomitant non-AED medications and AED medications
- 28-day total seizure frequency for the sum of individual seizures and clusters
- Percentage of both individual seizure free and cluster free days

All of the safety tables provided for the main 26-week open-label period will also be provided for the 52-week OLE.

The concomitant medications summary will include only those medications taken during the OLE period; i.e., those taken on or after the first dosing day of the OLE period and, for those subjects who enter the extension of the OLE, before the first dosing day of that extension.

The seizure endpoints will be based on both 6 and 12 months of OLE experience. The 6-month endpoints will be derived based on the first dosing day of OLE treatment through the last day of OLE treatment or 6 months of OLE treatment, whichever is earlier. The 12-month endpoints will be derived based on the first dosing day of OLE treatment through the end of the study, or if the subject enters the extension of the OLE, through the last day of OLE treatment.

Only the MITT population will be used for the efficacy analyses.

The adverse events will be summarized over just the OLE period as well as over the entire study (26-week main study and OLE periods). The summarizations over just the OLE period will include only those AEs that start or worsen on or after the first dosing day of GNX in the OLE period and, for subjects who enter the extension of the OLE period of the study, before the first

dosing day of that extension. The summarizations over the entire study will include AEs that start or worsen on or after the first dosing day of GNX and, for subjects who enter the extension of the OLE period of the study, before the first dosing day of that extension. Just the TEAEs will be summarized; there will be no table of pre-treatment emergent AEs.

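### Extension seizure results are measured against the same baseline that selected the children into the extension, so the table shows a reduction even with no drug effect, and it would carry the MITT label

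*Protocol*

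**What the plan says.** **Entry rule.** Protocol 9.3.2, item 10, admits to the OLE only children who completed all scheduled visits and "have shown a minimum 35% improvement in mean seizure frequency per 28 days", judged "vs. baseline over the 28 day periods preceding study entry". The SAP repeats the rule in Table 1, note 4 (children must "have shown a minimum 35% improvement in mean seizure frequency per 28 days vs. baseline"), without the phrase about the window.

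**Outcome.** SAP Section 9 states: "Baseline for the OLE period is the same as for the main period". Its listed OLE efficacy tables are "28-day total seizure frequency for the sum of individual seizures and clusters" and the percentage of days free of both seizures and clusters.

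**Who contributes.** OLE counting starts at the first OLE dose: "The 12-month endpoints will be derived based on the first dosing day of OLE treatment through the end of the study" (or, for children who go on to the further extension, through the last day of OLE treatment). SAP 2.5 rules out imputation unless otherwise specified: "All analyses will be based on available data". A child who did not enter therefore has no OLE value.

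**Label.** SAP Section 9 says: "Only the MITT population will be used for the efficacy analyses". SAP 2.2.2 defines MITT as every dosed child with at least one post-baseline diary day, and SAP 12.1 requires each table title to name its population. SAP 2.1 has the OLE analysed and reported apart from the main period, and SAP 1.3.2 confirms there is no control group.

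**The concern.** One recorded number, the child's baseline frequency, is the denominator of both the entry test and the OLE outcome. If it was high by chance, the child is more likely to pass the test and the later percent change is more negative. With no control arm, nothing in the OLE table separates this from a lasting drug effect.

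The label makes it worse. A table headed MITT suggests all treated children with diary data, whereas it can hold only those already seen to improve by 35%. The SAP defines no OLE-entrant set, plans no main-period column restricted to entrants, and gives no caveat on selection. What is at stake is the reading of the extension result, which runs to week 78 (26 + 52).

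**Working it through.** The plan gives no variance, effect size or OLE hypothesis, so there is no stated figure to reproduce. The check asks what the OLE table would show if the drug did nothing.

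**1. Mechanism.** Let B, M and O be a child's 28-day frequency at baseline, in the main period and in the OLE.
- Entry: M/B ≤ 1 - 0.35 = 0.65.
- Outcome: 100 × (O/B - 1).

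Take a child whose underlying rate λ never changes.
- If M and O both sit at λ, the child qualifies when B ≥ λ/0.65 = 1.54λ. The OLE change is then -35% or beyond, with no effect at all.
- If B sits at λ and M is low by chance (M ≤ 0.65λ), the OLE change from baseline is 0%, but the change from main period to OLE is at least 1/0.65 - 1 = +54%.

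The first route biases the planned table downward. The second biases a main-to-OLE comparison upward. Entrants are a mixture of the two.

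**2. Inputs from the documents.** 35% threshold; baseline of 4 to 12 weeks (Protocol 9.5.1); at least 4 seizures per 28 days (one of the alternative criteria in Protocol 9.3.2, item 4); 26 weeks of treatment; 52-week OLE.

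**3. Assumptions.** Seizure rates and their variability are assumed and varied. The 35% window is ambiguous, so three readings were run.
- Model A: Poisson counts, 8 to 60 seizures per 28 days, independent log-normal period effects with CV 20-60%.
- Model B: Poisson monthly counts, between-child median of 10 or 40 per 28 days (log-SD 1.0), within-child monthly log-SD 0 to 1.0, lag-1 correlation 0 to 0.5.

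**4. Results with zero drug effect, children who pass the rule**

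| Model | 35% judged over | OLE median change | OLE mean change |
|---|---|---|---|
| A | whole main period | -24% to -41% | -19% to -31% |
| B | whole 26 weeks | -27% to -54% | -23% to -45% |
| B | last 3 × 28 days | -25% to -44% | -22% to -34% |
| B | last 28 days | -17% to -34% | -11% to -23% |
| Independent months, 12-week baseline | last 28 days | -10% to -14% | -7% to -10% |

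Under the null, 7-37% of children pass in Model A. In Model B, 1-36% pass on the whole-period reading and up to 45% on the last-28-days reading.

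**5. Is the entry rule the cause?** In the whole-26-week null runs of Model B, the main-period median for unselected children was -11% to +30%. One example: median 10 per 28 days, log-SD 0.5, correlation 0.5, 12-week baseline. The unselected main-period median is -3%, 21% pass, and their OLE median is -35%. With a 4-week baseline the figures are -4%, 25% and -44%. Dropping the minimum-seizure criterion still leaves an OLE median of -30% to -38%.

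**6. Opposite bias.** In Model A the entrants' main-period median is -41% to -58%, because they were chosen for a low M. Their median within-child change from main period to OLE is +26% to +61% although nothing has changed.

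**The case against.** Several points against this are fair.

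- **Size is not fixed by the documents.** On the mildest reading (12-week baseline, independent months, last 28 days) the null median is only -10% to -14%. This stands, so no single figure should be quoted.
- **The entry measure and the endpoint may differ.** The rule refers to mean seizure frequency, while the SAP endpoint counts a cluster once (SAP 1.2.1), which SAP Section 11 records as a departure from what the protocol implied. The simulations treat the two as identical and may overstate the effect in children whose seizures are mainly in clusters. This stands.
- **Much is already visible.** Main-period results are listed per subject against the same baseline (SAP 6.1), OLE disposition is tabulated, and the entry rule is printed. A careful reader could reconstruct the selection. But the reports are separate and the OLE table would still be headed MITT, so this softens the point without removing it.
- **The OLE is descriptive.** True, and no OLE hypothesis or durability claim appears in either document. A reader might infer that the sponsor plans to claim sustained efficacy at 18 months; the text does not say so.
- **Responder rates.** A reader might take from the null runs that up to 41% of entrants would be reported as 50% responders. SAP Section 9 does not list an OLE responder table, and SAP 6.2.9 defines responders over the 26-week period, so that figure does not describe a planned output.

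The protocol supplied predates the Amendment 8.1 that the SAP cites, but the SAP carries the same 35% rule.

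**Conclusion.** The point holds as one about labelling and interpretation of the OLE efficacy tables. Followed exactly, SAP Section 9 produces a change from baseline that selection inflates, under a population name that hides the selection. The direction needs only that recorded baselines carry some chance variation, and every null scenario run gave a negative OLE median and mean. The size, roughly -10% to -54% at the median, rests on assumed rates and variability, on baseline length and on the reading of the 35% window. For scale only, the Protocol's introduction reports a 26% median decrease on ganaxolone and 10.2% on placebo in its largest controlled epilepsy study.

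Two stronger readings are tempting and unsupported. One is that the whole OLE reduction would be an artefact: the rule also selects children who truly respond, and the null runs show only what could appear without any effect. The other is that the trial's main result is biased by this rule: the primary 26-week MITT analysis comes before the selection and is unaffected by it.

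**What to change.** Change SAP Section 9 only; the entry rule need not be touched.

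1. Label the OLE efficacy population as MITT subjects who met the 35% entry rule and entered the OLE, not as MITT.
2. Give, per cohort, the number of entrants out of all MITT subjects.
3. For the same entrants, show baseline, main-period and OLE values side by side, with percent change from baseline for each period.
4. State with the table that selection inflates the OLE change from baseline, and that this change cannot alone be read as maintained efficacy.
5. Do not present the within-child change from main period to OLE as evidence of lost effect, since it regresses upward for the same reason. If it is shown, say so beside it.
6. If OLE responder proportions are reported, also give them with all MITT subjects as denominator and non-entrants as non-responders. In Model A this cuts the null 50% responder rate from 5-41% to 0.4-15% (share among entrants × share who pass). It needs an explicit exception to SAP 2.5.

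The cost is a few columns and a footnote built from values already derived under SAP 6.1. No new data are needed. The downside is that the OLE figures will look less favourable.
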